#### **9.3.2 Pharmacokinetic Statistical Methodology**

Log-transformed AUC (0- $\infty$ ), AUC(0- $t_{last}$ ), and  $C_{max}$  of lasmiditan will be evaluated in a linear mixed-effects model with fixed effects for period, sequence, and treatment and a random effect for participant within sequence.

#### Example SAS Code:

```
proc mixed data = xxx;
  by parameter;
  class treatment period sequence participant;
  model log_pk = treatment period sequence / cl residual;
  random participant(sequence);
  lsmeans treatment / cl pdiff alpha = 0.1;
  ods output lsmeans=lsmeans diffss=diffs;
run;
```

All valid PK data will be included, whether or not the participants completed all 3 periods.

Estimates of geometric least square (LS) mean ratios together with the corresponding 90% CIs will be derived for the comparisons of AUC (0- $\infty$ ), AUC(0- $t_{last}$ ), and  $C_{max}$  as follows:

- Primary endpoint: lasmiditan OD tablet without water (test) versus lasmiditan IR tablet
- Secondary endpoint: lasmiditan OD tablet with water (test) versus lasmiditan IR tablet.

The 2 lasmiditan formulations will be considered bioequivalent if the 90% CIs of the ratio of geometric LS means of AUC (0-∞), AUC(0-tlast), and Cmax falls completely within 0.80 to 1.25.

Values of tmax will be analyzed non-parametrically using the Wilcoxon signed rank test. Estimates of the median difference between test and reference formulations based on the observed medians, 90% CIs, and the p-value from the Wilcoxon test will be calculated.

Additional PK analyses may be conducted if deemed appropriate.

#### **9.4 Safety and Tolerability Assessments**

##### **9.4.1 Adverse events**

Where changes in severity are recorded in the Case Report Form (CRF), each separate severity of the AE will be reported in the listings, only the most severe will be used in the summary tables. A pre-existing condition is defined as an AE that starts before the participant has provided written informed consent and is ongoing at consent. A non-treatment emergent AE is defined as an AE which starts after informed consent but prior to the first dose. A TEAE is defined as an AE which occurs postdose or which is present prior to dosing and becomes more severe postdose.

All AEs will be listed. TEAEs will be summarized by treatment, severity and relationship to the study drug. The frequency (the number of AEs, the number of participants experiencing an AE and the percentage of participants experiencing an AE) of TEAEs will be summarized by treatment, Medical Dictionary for Regulatory Activities (MedDRA) version 23.0 system organ class and preferred term. The summary and frequency AE tables will be presented for all causalities and those considered related to the study drug by the investigator. Any SAEs will be listed.

Discontinuations due to AEs will be listed.

##### **9.4.2 Concomitant medication**

Concomitant medication will be coded using the WHO drug dictionary (Version MAR20B3). Concomitant medication will be listed.

##### **9.4.3 Clinical laboratory parameters**

All clinical chemistry, hematology, and urinalysis data will be listed. Additionally, clinical chemistry, hematology and urinalysis data outside the reference ranges will be listed and flagged on individual participant data listings.

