Abbreviations: CRU = clinical research unit; ECG = electrocardiogram; D = Day; ED = early discontinuation; h = hour; M8 = metabolite 8; OD = oral disintegrating; P = predose; PK = pharmacokinetic(s).

^a The Day 5 and Day 6 visits of a treatment period may occur at the same time as the Day -1 and Day 1 visits, respectively, of the subsequent treatment period. Therefore, assessments that occur on both visits will only be performed once. All results must be reviewed prior to dosing on Day 1 of each treatment period. The Day 6 visit of Treatment Period 3 will be considered the final visit.

2. Introduction

Lasmiditan (LY573144) has been developed by Eli Lilly and Company (Lilly), and approved by the Food and Drug Administration (FDA), for the acute treatment of migraine with or without aura in adults. Full details of the preclinical and clinical safety and tolerability data are contained in the Investigator's Brochure (IB).

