9.4. Statistical Analyses

Statistical analysis of this study will be the responsibility of the sponsor or its designee.

Any change to the data analysis methods described in the protocol will require an amendment only if it changes a principal feature of the protocol. Any other change to the data analysis methods described in the protocol, and the justification for making the change, will be described in the statistical analysis plan (SAP) and the clinical study report. Additional exploratory analyses of the data will be conducted as deemed appropriate.

The SAP will be finalized prior to the first participant visit and it will include a more technical and detailed description of the statistical analyses described in this section. This section is a summary of the planned statistical analyses of the most important endpoints including primary and key secondary endpoints.

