9.4.1. General Considerations

Data listings will be provided for all data that are databased. Data listings will be provided for all participants up to the point of withdrawal, with any participants excluded from the relevant population highlighted.

Summary statistics and statistical analysis will only be presented for data where detailed in the SAP. Summary statistics and statistical analyses will generally only be performed for participants included in the relevant analysis population. For the calculation of summary statistics and statistical analysis, unrounded data will be used.

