9.4.3.2. Statistical Evaluation of Safety

Safety parameters that will be assessed include safety laboratory parameters and vital signs. The parameters will be listed and summarized using standard descriptive statistics. Additional analysis will be performed if warranted upon review of the data.

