#### **9.4.8 Other assessments**

All other safety assessments not detailed in this section will be listed but not summarized or statistically analyzed.

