### **11. CHANGES FROM THE PROTOCOL SPECIFIED STATISTICAL ANALYSES**

There were no changes from the protocol specified statistical analyses.

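### Must the SAP add laboratory summary tables because the protocol says laboratory data will be listed and summarized?

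*SAP*

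**What the plan says.** Protocol 9.4.3.2 sets the scope: "Safety parameters that will be assessed include safety laboratory parameters and vital signs". Its next sentence gives the presentation: "The parameters will be listed and summarized using standard descriptive statistics". It adds that further analysis will follow if review of the data warrants it.

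SAP 9.4.3 covers laboratory data: "All clinical chemistry, hematology, and urinalysis data will be listed". Values outside the reference range are also listed and flagged. No table of summary statistics is mentioned. SAP 9.4.4, by contrast, summarizes vital signs by treatment, with change from the Day 1 predose value of each period. Under SAP 9.4.7, laboratory data from hepatic follow-up are listed. SAP 9.4.8 closes the remainder: "All other safety assessments not detailed in this section will be listed but not summarized or statistically analyzed".

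Four passages decide which text governs and how differences are recorded:

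- Protocol 9.4.1: "Summary statistics and statistical analysis will only be presented for data where detailed in the SAP". SAP 9.1 repeats this.
- SAP section 3 says the SAP takes precedence over the protocol's statistical section, and that substantial differences will be identified.
- Protocol 9.4 says that any non-principal change to the analysis methods, "and the justification for making the change, will be described in the statistical analysis plan (SAP) and the clinical study report".
- SAP section 11: "There were no changes from the protocol specified statistical analyses".

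**The concern.** The protocol sentence carries no condition. The proviso about the frequency of events stands in 9.4.3.1, on clinical evaluation, and does not reach 9.4.3.2. On its face, then, the protocol specifies a descriptive laboratory summary that the SAP leaves out, while SAP section 11 reports no departure.

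Two things would be at stake. One is the record: if listing instead of summarizing counts as a change of method, Protocol 9.4 asks for it to be described and justified. The other is the safety review. Listings show one participant at a time, so a small shift common to many participants, with each value still inside its reference range, is harder to see than in a table of means before and after dosing. Such a table would give context for the secondary objective on safety and tolerability.

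**Working it through.** The plan states no figure to reproduce here. The check is a comparison of texts, with one count to fix the scope.

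**1. Do the texts differ?**

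| Parameter class named in Protocol 9.4.3.2 | Protocol | SAP |
|---|---|---|
| Vital signs | list and summarize | listed and summarized (9.4.4) |
| Safety laboratory parameters | list and summarize | listed, out-of-range values flagged (9.4.3) |

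The SAP text carries out the summary for 1 of 2 classes. Sections 9.4.7 and 9.4.8 do not supply the other, and section 9.1 rules out summaries that the SAP does not detail. So the texts differ.

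**2. Is listings-only allowed?** Protocol 9.4.1 makes the SAP the place where summaries are chosen, and SAP section 3 gives the SAP precedence. Read with these, 9.4.3.2 can be taken as the general intention and the SAP as the detail. An analyst would know which text to follow: produce the listings. The weakness of this reading is that it leaves the words on summarizing in 9.4.3.2 with no effect for laboratory data.

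**3. How much data?** The Schedule of Activities puts clinical laboratory tests on Day -1 and at 24 h in each period.

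- Per participant: 2 samples × 3 periods = 6. This matches the 6 clinical laboratory samples in the blood sampling table of Protocol 10.2.1 (6 × 12.5 mL = 75 mL).
- Planned completers: 36 × 6 = 216 scheduled samples. If all 48 enrolled completed: 48 × 6 = 288.
- These counts leave out screening, early-discontinuation and repeat samples. A participant who left after the 24 h sample of Period 3 could have 6 + 1 = 7.

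**4. Does any result change?**

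- The primary and secondary PK comparisons rest on Cmax and the two AUCs, with 90% CIs held against 0.80 to 1.25. Laboratory data do not enter.
- The endpoint for the safety objective (Protocol section 3, SAP 4.2) is the incidence of TEAEs and SAEs. Laboratory means are not an endpoint.
- Protocol 8.2.4 has the investigator record clinically relevant laboratory changes in the AE section of the eCRF, and Protocol 10.3.1 counts clinically significant abnormal results as AEs. SAP 9.4.1 summarizes TEAEs by treatment, severity and relationship to drug. Laboratory changes that matter clinically, and that are treatment-emergent, therefore reach a by-treatment table.
- SAP 9.4.9 plans no inferential safety analysis, so no test or interval is lost.

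**5. Would a summary need new rules?** No laboratory test is scheduled on Day 1, so the vital-sign baseline cannot simply be borrowed. Day -1 of Periods 2 and 3 may also fall on Day 5 of the period before, in which case "Therefore, assessments that occur on both visits will only be performed once". A table by treatment, or of change from baseline, would need a convention for those shared visits, up to 2 of the 3 Day -1 samples. Protocol 9.4.3.2 asks for neither layout. A plain summary by scheduled time point would satisfy it and needs no such convention.

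**The case for a change.** The strongest case for a change is that a specific sentence should prevail over a general clause. Protocol 9.4.3.2 names laboratory parameters and says they will be summarized, whereas 9.4.1 speaks of summaries in general. SAP section 3 asks only for substantial differences to be identified, but Protocol 9.4 sets no such threshold for non-principal changes. On that reading SAP section 11 is inaccurate on this point, and one added sentence in 9.4.3 or one entry in section 11 would cure it at almost no cost.

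Most of this stands as a matter of wording. The sections do not say the same thing, and the statement of no changes is hard to square with a strict reading of Protocol 9.4. It can still be argued that choosing a listing over a table is not a change of analysis method, given that 9.4.1 leaves that choice to the SAP.

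What does not stand is the step from wording to consequence. The only loss is a convenient descriptive view of values that are all listed in any case. Protocol 9.4.3.2 also leaves room for more analysis if review of the listings suggests a need.

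**Conclusion.** The mismatch is real, and it is clerical. One of the two parameter classes named in Protocol 9.4.3.2 has no summary planned in the SAP text, and SAP section 11 does not mention it. No endpoint, interval or conclusion depends on it. The data at issue are 6 scheduled samples per participant, all of them listed and flagged when out of range, and clinically significant changes are captured through AE reporting. Adding tables would bring the two documents into line but would not alter what the trial can conclude.

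The conclusion rests on two assumptions. The first is that investigators record clinically significant laboratory changes as AEs, as Protocol 8.2.4 and 10.3.1 require. The second is that the laboratory listings are complete. The table and listing shells and the clinical study report were not available. The shells might already contain a laboratory summary and the report might note the difference, so nothing is claimed about either.

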##### **9.4.4 Vital signs**

Vital signs data will be summarized by treatment together with changes from baseline, where baseline is defined as the Day 1 predose assessment within each period. Figures of mean vital signs and mean changes from baseline profiles will be presented by treatment.

Values for individual participants will be listed.

#### **9.4.5    Electrocardiogram**

All ECGs will be performed for safety monitoring purposes only and will not be presented. Any clinically significant findings from ECGs will be reported as an AE.

#### **9.4.6    Product Acceptability and Palatability Analyses**

Participants will be asked to provide responses to questions designed to assess the acceptability and palatability of the OD tablet when administered with and without water. The questionnaire will be completed by the participant immediately after administration of the OD tablet both with and without water, and will assess the participants' experience relating to the taste, smell, mouthfeel, aftertaste, and the approximate disintegration time of the OD tablet in the oral cavity.

Responses from the product acceptability and palatability questionnaire will be summarized categorically (frequency and percentage) by treatment, and listed.

#### **9.4.7    Hepatic Monitoring**

##### **Close hepatic monitoring**

If a participant who had normal or near normal baseline alanine aminotransferase (ALT), aspartate aminotransferase (AST), alkaline phosphatase (ALP), total bilirubin (TBL) (i.e.,  $<1.5 \times$  upper limit of normal [ULN]), experiences elevated  $ALT \geq 3 \times$  ULN,  $AST \geq 3 \times$  ULN,  $ALP \geq 2 \times$  ULN, or  $TBL \geq 2 \times$  ULN, laboratory tests should be repeated within 48 to 72 hours, including ALT, AST, ALP, TBL, direct bilirubin, gamma-glutamyltransferase, and creatinine kinase to confirm the abnormality and to determine if it is increasing or decreasing.

In participants enrolled with elevated baseline ALT, AST, ALP or TBL ( $\geq 1.5 \times$  ULN), the thresholds for close monitoring are  $ALT \geq 2 \times$  baseline,  $AST \geq 2 \times$  baseline,  $ALP \geq 2 \times$  baseline, or  $TBL \geq 2 \times$  baseline.

At a minimum, this evaluation should include physical examination and a thorough medical history, including symptoms, recent illnesses, (for example, heart failure, systemic infection, hypotension, or seizures), recent travel, history of concomitant medications (including over-the-counter), herbal and dietary supplements, history of alcohol drinking and other substance abuse.

If the abnormality persists or worsens, clinical and laboratory monitoring, and evaluation for possible causes of abnormal liver tests should be initiated by the investigator in consultation with the Lilly-designated medical monitor.

##### **Comprehensive hepatic evaluation**

If a study participant, who had baseline ALT, AST, ALP, TBL  $< 1.5 \times$  ULN, experiences elevated  $ALT \geq 5 \times$  ULN,  $AST \geq 5 \times$  ULN,  $ALP \geq 3 \times$  ULN,  $TBL \geq 2 \times$  ULN, or elevated ALT, AST  $\geq 3 \times$  ULN with hepatic signs/symptoms (severe fatigue, nausea, vomiting, right upper quadrant abdominal

pain, fever, rash, and/or eosinophilia $>5\%$ ), a comprehensive evaluation should be performed to search for possible causes of liver injury.

In participants who had elevated baseline ALT, AST, ALP, or TBL ( $\geq 1.5 \times$  ULN), the thresholds for performing this evaluation are ALT $\geq 3 \times$  baseline, AST $\geq 3 \times$  baseline, ALP $\geq 2 \times$  baseline, TBL $\geq 1.5 \times$  baseline, or ALT, AST  $\geq 2 \times$  baseline with hepatic signs/symptoms.

At a minimum, this evaluation should include physical examination and a thorough medical history, as outlined above, as well as tests for prothrombin time-international normalized ratio, viral hepatitis A, B, C, E, tests for autoimmune hepatitis, and an abdominal imaging study (for example, ultrasound or computed tomography scan).

### **Additional hepatic data collection in participants who have abnormal liver tests during the study**

Additional hepatic safety data collection should be performed in participants who meet 1 or more of the following 5 conditions:

1. Elevation of serum ALT to  $\geq 5 \times$  ULN on 2 or more consecutive blood tests (if baseline ALT $<1.5 \times$  ULN)
  - In participants with baseline ALT $\geq 1.5 \times$  ULN, the threshold is ALT $\geq 3 \times$  baseline on 2 or more consecutive tests
2. Elevation of TBL to  $\geq 2 \times$  ULN (if baseline TBL  $<1.5 \times$  ULN)
  - In participants with baseline TBL  $\geq 1.5 \times$  ULN, the threshold should be TBL  $\geq 2 \times$  baseline
3. Elevation of serum ALP to  $\geq 2 \times$  ULN on 2 or more consecutive blood tests (if baseline ALP  $<1.5 \times$  ULN)
  - In participants with baseline ALP $\geq 1.5 \times$  ULN, the threshold is ALP  $\geq 2 \times$  baseline on 2 or more consecutive blood tests
4. Hepatic event considered to be an SAE
5. Discontinuation of the investigational product due to a hepatic event.

Where applicable, the following will be presented. The participants' liver disease history and associated person liver disease history data will be listed. Any concomitant medications that have potential for hepatotoxicity, including acetaminophen will be listed. Results from any hepatic monitoring procedures, such as a magnetic resonance elastography scan, and biopsy assessments will be listed, if performed.

Hepatic risk factor assessment data will be listed. Liver related signs and symptoms data will be summarized by treatment and listed. Alcohol and recreational drug use data will also be listed.

All hepatic chemistry, hematology, coagulation, and serology data will be listed. Values outside the reference ranges will be flagged on the individual participant data listings.

#### **9.4.8 Other assessments**

All other safety assessments not detailed in this section will be listed but not summarized or statistically analyzed.

#### **9.4.9 Safety and Tolerability Statistical Methodology**

No inferential statistical analyses are planned.

### **10. INTERIM ANALYSES**

No interim statistical analyses are planned.

### **11. CHANGES FROM THE PROTOCOL SPECIFIED STATISTICAL ANALYSES**

There were no changes from the protocol specified statistical analyses.

### **13. DATA PRESENTATION**

#### **13.1 Derived Parameters**

Individual derived parameters (e.g. PK parameters) and appropriate summary statistics will be reported to three significant figures. Observed concentration data, e.g.  $C_{max}$ , should be reported as received. Observed time data, e.g.  $t_{max}$ , should be reported as received. N and percentage values should be reported as whole numbers. Median values should be treated as an observed parameter and reported to the same number of decimal places as minimum and maximum values.

#### **13.2 Missing Data**

Missing data will not be displayed in listings.

---

### 13.3 Insufficient Data for Presentation

Some of the TFLs may not have sufficient numbers of participants or data for presentation. If this occurs, the blank TFL shell will be presented with a message printed in the center of the table, such as, "No serious adverse events occurred for this study."

Leo Document ID = 2049b77a-30e0-4d19-955c-ed1c7f41d078

Approver: PPD

Approval Date & Time: 09-Mar-2021 09:41:39 GMT

Signature meaning: Approved

Approver: PPD

Approval Date & Time: 09-Mar-2021 12:34:43 GMT

Signature meaning: Approved

Approver: PPD

Approval Date & Time: 09-Mar-2021 15:44:48 GMT

Signature meaning: Approved

Approver: PPD

Approval Date & Time: 10-Mar-2021 15:20:55 GMT

Signature meaning: Approved
